3.4. Measures

Primary dependent variables :

Relapse and total abstinence measured at several defined times: two weeks, one month, three months, six months and one year after treatment..

Secondary dependent variables:

- Craving measured before and after each tDCS session via visual analog scales, such as Likert -100 to +100, as well as the *Alcohol Urge Questionnaire* (AUQ) with 8 items. Craving will also be measured in T1 and T2 through the *Craving Experience Questionnaire* (CEQ);

- Symptoms of depression with the *Beck Depression Inventory* (BDI-II) and positive and negative affectivity with the Positive and Negative Affect Schedule (PANAS) measured at T1 and T2;
- Anxiety trait in T1 and T2 with the *State Anxiety Inventory* (STAI-A).
- The working memory performance measured in T1 and T2 with the span reversed.
- Inhibitory control evaluated by performance at a Go/Nogo task and its event-related potential (Nogo N2 and Nogo P3). This measurement will be carried out as part of a clinical examination (cognitive and neurophysiological battery with an electroencephalogram) offered to patients during their hospitalization at Unit 72. This review will be conducted before and after the intervention (in T1 and T2).

All the questionnaires were in French version.

Metacognition items:

At the end of the experiment, patients will be asked orally (1) Do you think you are in the active tDCS group?, (2) Would you be interested in continuing this intervention over a longer period of time?

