2. HYPOTHESES

For patients with AUD, the intervention of five sessions of tDCS during a detoxification:

- decreases the relapse rate 2 weeks after the treatment;
- decreases patient craving;
- improves depression and anxiety;
- strengthens inhibitory capacities.

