3.2. Procedure

During the first two weeks of hospitalization, the study will be offered to patients. If they accept, a first semi-structured interview will be organized to explain the study, sign the informed consent, collect more information and verify the inclusion and exclusion criteria. During this interview, the demographic characteristics (age, sex and level of education), history with alcohol (number of years of dependence, number of previous treatment, etc.), frequency and amount of alcohol consumed before treatment, psychiatric history, etc. The DSM 5 criteria will be verified, and patients will complete these questionnaires in French version: *Alcohol Use Disorder Identification Test (AUDIT)*, *Impulsivity Behavior Scale (UPPS-P)* and *Trait Anxiety Inventory (STAI-B)*.

From Monday to Friday of the third week of hospitalization, patients will receive the procedure. Five consecutive 20 minute days of tDCS, either active or sham. Before and after each session, the tie will be measured using analog visual scales. To measure the effects of tDCS, on the Friday preceding (T1) and the Monday following (T2) the intervention week,

patients will respond to a battery of questionnaires and cognitive tasks during the recording of evoked potentials (via an electroencephalogram). T1 and T2 will each last approximately one hour.

Figure 1: Study plan. Day 1 is theoretically the first day of hospitalization and the procedure takes place between Day 15 and 19.

In order to observe whether specific neural changes underlie relapse and abstinence, evoked potentials will be acquired for each participant at two points, before the start of the stimulation by tDCS and once the five sessions have been completed.

Once hospitalization is complete, patients will be followed by telephone call to find out the status of their abstinence and/or alcohol consumption. The call will be made via Unit 72 personnel.

Recruitment would start if possible at the end of March 2021 for a period of 12 months. Based on our estimates based on the performance of the previous study, five patients will be recruited per month.

[figure not shown]
3.3. tDCS

During the neuromodulation session, the patient will watch nature documentaries, cut into 5 episodes of 20 minutes.

The configuration of tDCS is based on recommendations in the literature (Fregni et al., 2020; Lefaucheur et al., 2017).

- 5 sessions of bilateral stimulation of the dlPFC;

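### Section 3.4 measures the CEQ at T1 and T2 but Table 1 marks it only at the Day 3-4 interview; if Table 1 is followed, the planned T1-versus-T2 analysis cannot be run on it

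*Combined protocol and SAP*

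**What the plan says.** Section 2 lists four hypotheses for the intervention, one of which is that it "decreases patient craving". Three instruments serve that hypothesis: the VAS, the AUQ and the CEQ.

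- **Visits.** Section 3.2 fixes the assessment points: "To measure the effects of tDCS, on the Friday preceding (T1) and the Monday following (T2) the intervention week". Table 1 dates them Day 12 and Day 22, either side of the sessions on Days 15 to 19.
- **CEQ.** Section 3.4: "Craving will also be measured in T1 and T2 through the *Craving Experience Questionnaire* (CEQ". Table 1 has a single mark for it, in the interview column (Day 3-4).
- **Interview list.** Section 3.2 says that at this interview "patients will complete these questionnaires in French version: *Alcohol Use Disorder Identification Test (AUDIT)*, *Impulsivity Behavior Scale (UPPS-P)* and *Trait Anxiety Inventory (STAI-B". The CEQ is not among the three.
- **Sessions.** Section 3.4: "Craving measured before and after each tDCS session via visual analog scales", and after the scale range it adds "as well as the *Alcohol Urge Questionnaire* (AUQ) with 8 items". Section 3.2 names one type of instrument at the sessions: "Before and after each session, the tie will be measured using analog visual scales". I take the object of that sentence to be craving. Table 1 marks the VAS at T1, the sessions and T2, and the AUQ at T1 and T2 only.
- **Analysis.** Section 3.5 gives the secondary measures one analysis, a mixed ANOVA with Time (T1, T2) and Condition (active, sham) as factors.

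**The concern.** The text and the schedule table give different times for a named secondary outcome, and the planned analysis works with only one of them. Table 1 presents itself as the list of what will be collected, so staff could reasonably work from it. In that case no CEQ is taken after stimulation. A questionnaire about craving on the Monday after the intervention week cannot be collected later, so the loss could not be repaired once a patient has passed T2. The Day 3-4 value could not stand in: it falls 8 to 9 days before T1 (12 − 4 and 12 − 3) and has no later value to be compared with.

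The AUQ raises a similar but looser question: whether it belongs to the sessions, to T1 and T2, or to both.

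**Working it through.** No sample-size or power figure is involved. The check sets the schedules side by side and counts what each one delivers to the analysis in 3.5, which needs a value at both T1 and T2.

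| Instrument | Section 3.2 | Section 3.4 | Table 1 |
|---|---|---|---|
| CEQ | not named; absent from the interview list | T1, T2 | Day 3-4 interview only |
| AUQ | not named | with the VAS at the sessions (natural reading) | T1, T2 |
| VAS | sessions | sessions | T1, sessions, T2 |

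**CEQ.** Under 3.4 there are 2 usable administrations per patient, and 2 × 60 = 120 with full attendance. Under Table 1 there is 1 administration, before T1, so 0 of the 2 required time points. No change score is possible either.

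**AUQ.** On the natural reading of 3.4 there are 5 sessions × 2 = 10 administrations per patient and none stated at T1 or T2. Table 1 gives 0 at the sessions and 2 at T1 and T2. On that reading the ANOVA on the AUQ depends on Table 1.

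**VAS.** There is no conflict. Table 1 keeps the sessions named in 3.2 and 3.4 and adds T1 and T2.

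**What each source supports.** Following Table 1 throughout, 2 of the 3 craving instruments (VAS, AUQ) have both time points. Following 3.4 throughout, on the reading above, only the CEQ has them. Neither source can simply be declared to override the other.

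**Visit load.** Table 1 marks seven items at T1: STAI-A, VAS, AUQ, PANAS, BDI-II, reverse span and Go/Nogo. T2 has the same seven plus the metacognition questions, so 8. Adding the CEQ gives 7 + 1 = 8 at T1 and 8 + 1 = 9 at T2.

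**The case against.** The strongest reply is that this is a small scheduling slip. Explicitly, it is one statement against one. Only 3.4 places the CEQ at T1 and T2. Section 3.2 refers to an unnamed set of questionnaires at those visits, and 3.5 speaks of secondary measures in general. Both are compatible with 3.4, and the interview list in 3.2 lends Table 1 no support, but neither section names the CEQ. Nothing shows that the appendix table would be the working checklist. The outcome is secondary, and two other craving instruments have marks at both visits. All of this stands, and it limits the size of the point. It does not remove the contradiction, which nothing in the text resolves.

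A reader might infer that the CEQ analysis is impossible as the plan stands. That is too strong: it is impossible only if Table 1 governs. A reader might also infer that the craving hypothesis is lost. It is not, because the VAS and AUQ remain under Table 1.

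The AUQ mismatch should not be read as an equally firm contradiction. It depends on letting the timing at the start of the sentence in 3.4 carry over to "as well as the *Alcohol Urge Questionnaire* (AUQ) with 8 items". That is the natural reading, but the wording is loose. Section 3.2 and Table 1 agree in giving no AUQ at the sessions.

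Finally, a mark could have been lost from the CEQ row when the table was read from PDF, and Figure 1 (the study plan) is not shown. A lost mark is unlikely: the row sits among the interview-only rows, between AUDIT and UPPS-P, and its neighbours align with their columns.

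**Conclusion.** The CEQ inconsistency is real and should be corrected before recruitment. Its size is conditional: 2 usable CEQ administrations per patient if 3.4 is followed, 0 if Table 1 is followed. In the second case one of three craving instruments drops out of the planned analysis and cannot be recovered afterwards. The AUQ point is weaker and costs no planned T1-versus-T2 test if Table 1 is followed.

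The conclusion assumes that the CEQ row of Table 1 was read correctly and that Figure 1 does not settle the timing. The 120 administrations assume that all 60 patients attend both visits.

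**What to change.** Before recruitment:

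1. In Table 1, mark the CEQ at T1 and T2, to agree with 3.4 and with the analysis in 3.5. Keep the Day 3-4 mark only if an extra baseline is intended, and then add the CEQ to the interview list in 3.2.
2. In 3.4, state that the VAS and AUQ are taken at T1 and T2, as Table 1 shows.
3. Decide whether the AUQ is also given at the sessions, and make 3.2, 3.4 and Table 1 say the same. Either limit the session measure in 3.4 to the VAS, or add the AUQ to 3.2 and to the Sessions column.

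The editing cost is a few table cells and sentences. The practical cost is one more questionnaire at T1 and at T2 than Table 1 lists. Section 3.4 already asks for it, but the length of the CEQ is not given. The sponsor should check that it fits, since "T1 and T2 will each last approximately one hour". If the AUQ is kept at the sessions, it adds 10 administrations × 8 items = 80 item responses per patient that 3.2 and Table 1 do not provide for.

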3.5. Statistical analyses

Primary measurement: In order to respond to our primary assumptions about relapse, we will perform logistic regressions with the independent variable conditions (tDCS active scored 1 and tDCS sham scored -1) and the variable dependent relapse at each measurement (2 weeks, 1 month, 3 months, 6 months and 1 year). A Kaplan-Meier survival analysis will be performed on the number of days prior to relapse to compare the curves up to one year of follow-up.

Finally, in order to compare our two conditions to the four conditions of the previous study, we will perform a logistic regression with linear polynomial contrasts (combined active tDCS with ICT > tDCS only > tDCS sham).

Secondary measures: In order to respond to our secondary assumptions about the variables before and after the intervention, we will perform mixed repeated measures ANOVAs [Time (T1 vs. T2) x Condition (tDCS active vs. tDCS sham)].

4. Benefits

At the individual level, stimulation by tDCS could on the one hand help patients to prolong alcohol abstinence time and on the other have positive effects on mood, especially an improvement in the level of anxiety and depression.

In a broader sense, this study will contribute to a better definition of the mechanisms involved in abstinence and in the phenomenon of relapse of alcohol use disorders. It will also compare whether tDCS is more effective alone or combined with cognitive training. The purpose of this study is to support medical research to improve management for people with alcohol dependence.

5. Safety and tolerability of tDCS

The tolerance of tDCS will be assessed during stimulation with an likert scale. A short questionnaire reporting possible side effects will be distributed to all participants to record the symptoms caused by stimulation.

The most common side effects include tingling, itching, and mild erythema. Although they are less frequent, the perception of a feeling of discomfort or burning, as well as the occurrence of a headache, are also possible events. These are side effects that are well tolerated, essentially limited to the time of stimulation and do not require medical treatment. Severe adverse effects or late onset were not identified.

6. Ethics

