3. PROTOCOL

3.1. Patients

This is a clinical trial that is part of an alcohol detoxification cure at Unit 72 Addictology of CHU Brugmann. The idea is to add a neuromodulation intervention to the initial management, multidisciplinary and psycho-bio-social. This will be a randomized, sham-controlled, single-blind study.

A total of 60 subjects will be recruited according to the inclusion and exclusion criteria. They will be randomly divided into two groups: the 'active' group (A) that will benefit from tDCS stimulation and the 'sham' group (S).

Exclusion criteria:

- Personal history of epilepsy;
- Have metal head implants that counter-indicate electrical stimulation;
- Diagnosis of chronic psychotic disorder, schizophrenia or bipolar type 1 disorder;
- Use of alcohol or other illicit substances during the experiment;
- Hair incompatible with neuromodulation.

[figure not shown]

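### Relapse is tested as primary at five times with no error control although the hypothesis names 2 weeks only, so the chance of a false primary claim is about 13–18% instead of 5%

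*Combined protocol and SAP*

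**What the plan says.** All references are to the combined protocol and SAP.

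- **Section 2 (Hypotheses)** has one relapse hypothesis: the intervention "decreases the relapse rate 2 weeks after the treatment". No later time is mentioned.
- **Section 3.4 (Measures)** gives as primary variables: "Relapse and total abstinence measured at several defined times: two weeks, one month, three months, six months and one year after treatment". The five times are not ranked.
- **Section 3.5 (Statistical analyses)**, in the part on the primary measurement, says: "In order to respond to our primary assumptions about relapse, we will perform logistic regressions". The outcome is "the variable dependent relapse at each measurement (2 weeks, 1 month, 3 months, 6 months and 1 year", which means five regressions. It adds: "A Kaplan-Meier survival analysis will be performed on the number of days prior to relapse", to compare the curves up to one year.

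Nowhere does the document state a significance level, sidedness, testing order, multiplicity adjustment or a rule for calling the trial positive.

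**The concern.** The hypothesis and the primary analysis do not match. One question is posed, at 2 weeks, but five tests are offered to answer it and none is marked as decisive. Read as written, a significant result at any of the five times is a positive primary result.

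Two things are at stake. The type I error of the main claim is not controlled. In addition, a result at three months, say, with nothing at 2 weeks could be presented as success, although it would address neither the stated hypothesis nor the two-week finding of the group's earlier trial (section 1), with which this study is meant to be compared.

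**Working it through.** The plan gives no error rate or power calculation, so there is no figure of its own to reproduce.

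**Inputs from the document**
- Five primary logistic tests (section 3.5).
- Sample size: "A total of 60 subjects will be recruited" (section 3.1). This equals the expected accrual in section 3.2, 5 per month × 12 months = 60.
- Two randomised groups, ratio not stated (section 3.1).

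**Assumptions, because the document is silent**
- 30 patients per arm.
- Two-sided 5% per test, unadjusted.
- Relapse is cumulative: once relapsed, a patient counts as relapsed at every later time.
- Any one significant time counts as a primary success.
- Relapse patterns as listed below.

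**Step 1. Reference value under independence.** 1 − 0.95^5 = 0.226, or 22.6%. The five tests are positively correlated, so the true value is lower.

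**Step 2. How strongly they are correlated.** For cumulative relapse proportions F_s < F_t, the correlation of the two test statistics is √[F_s(1 − F_t) / (F_t(1 − F_s))]. With 25% relapsed at 2 weeks and 37% at one month this is √(0.25 × 0.63 / (0.37 × 0.75)) = 0.75. Between 25% at 2 weeks and 75% at one year it is √(0.25 × 0.25 / (0.75 × 0.75)) = 0.33.

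**Step 3. Simulation under no effect.** Both arms draw relapse times from the same distribution. Each of the five times is tested, and a trial counts as a false positive if any test is significant. With 100,000 trials for each of four patterns (15–40% relapsed at 2 weeks, rising to 60–85% at one year), the results were 13–14% (Wald), 15–16% (Pearson) and 17–18% (likelihood ratio).

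A separate run with 200,000 trials per pattern and six patterns gave:

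| Relapse at 2 wk, 1, 3, 6, 12 mo (%) | Wald | Pearson (score) | Likelihood ratio |
|---|---|---|---|
| 25, 37, 52, 62, 75 | 14.2% | 15.7% | 17.7% |
| 20, 35, 55, 70, 85 | 13.7% | 17.5% | 19.9% |
| 30, 45, 65, 80, 88 | 13.1% | 17.3% | 19.9% |
| 40, 50, 65, 75, 85 | 13.1% | 15.8% | 17.5% |
| 10, 20, 35, 50, 60 | 12.4% | 16.8% | 19.6% |
| 50, 60, 75, 85, 90 | 11.5% | 16.4% | 19.0% |

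In the same run the 2-week Pearson test alone rejected in 4.8–5.4% of trials, as it should.

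**Step 4. Check without a relapse model.** Five normal test statistics with equal pairwise correlation give 18.4% at 0.5, 14.9% at 0.7, 12.8% at 0.8 and 10.1% at 0.9.

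**Step 5. Where the excess comes from.** In null trials, a significant later time with nothing at 2 weeks occurred in 8–12%, against 2–6% for the 2-week test itself. Most false primary positives would therefore fall outside the stated hypothesis.

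**Step 6. The survival comparison.** Adding a log-rank test (assumed, as section 3.5 names none) raised the figures in the table by only 0.1 to 1.2 percentage points.

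**The case against.** The strongest reply is that section 2 already fixes the deciding time. It contains the only relapse hypothesis, the regressions are said to answer the primary assumptions about relapse, and the earlier trial's effect was also at 2 weeks. On that reading the later times describe durability and the error is about 5%. This may be what was meant, but sections 3.4 and 3.5 list all five times as primary and never make the later ones subordinate. Under this reading too, the text needs correcting.

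Second, the hypothesis is directional, and the figures count significance in either direction. Counting only results that favour active tDCS gives 5.7–6.9% (Wald), 7.6–8.4% (Pearson) and 8.5–9.8% (likelihood ratio). This is correct, but the benchmark halves as well, to 2.5%, so the roughly threefold inflation remains.

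Third, the range depends on assumptions and is not due to multiplicity alone. That stands. At this sample size a single 2-week likelihood-ratio test already rejects in 5.1–7.5% of null trials, while the Wald test can be very conservative when cells are small (down to 0.9%). The Pearson figures isolate the multiplicity best.

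Fourth, total abstinence has no test of its own in section 3.5 and may simply be the complement of relapse. It adds error only if it is defined differently and tested separately.

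Finally, this is a small single-unit study, and Bonferroni, Holm or a single time-to-relapse test would also control the error. Size does not remove the need for a decision rule, and the document does not describe the relapse analyses as exploratory. The choice of remedy is the sponsor's, but 2 weeks is the one that follows from the trial's own hypothesis.

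**Conclusion.** The concern holds. Followed as written, the plan gives about a 13–18% chance of at least one false primary finding, which is 2.6 to 3.6 times the conventional 5%. This rests on 30 per arm, two-sided 5% per test, cumulative relapse with moderate patterns, and any significant time counting as success. More extreme patterns widen the range to about 11–21%; every value is more than double 5%. If only the 2-week test were decisive the error would be nominally 5%, but the plan does not say so. This must be settled before outcome data are seen, because a deciding test chosen afterwards would not be credible.

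**What to change.** In sections 3.4 and 3.5, name relapse at 2 weeks as the single primary outcome, tested once at two-sided 5%, in line with section 2. State the level, the sidedness and which test supplies the p-value. Make relapse at 1, 3, 6 and 12 months, total abstinence and the time-to-relapse comparison secondary, and say whether total abstinence is just the absence of relapse. If confirmatory claims at later times are wanted, test them in a fixed sequence and only after a significant 2-week result.

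The cost is protocol wording; every time point is still collected and reported. The one real loss is that an effect appearing only later could not be called a primary success. Keeping all five as primary with Bonferroni (0.05/5 = 0.01 each) would also control the error, but at a price in power. As an illustration, with the 6-month abstinence rates cited in section 1 (50% versus 11.8%) and 30 per arm, power falls from 91% at 0.05 to 75% at 0.01.

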We conducted a first clinical trial at Unit 72 Addictology of CHU Brugmann between 2017 and 2020 (reference: CE 2017/117), which was funded by the King Baudouin Foundation (ref: 2016-J1130650-206500) and then by the Brugmann Foundation (fund 2020-2021) (article in writing, pre-registered: <https://clinicaltrials.gov/ct2/show/NCT03447054>). The study had a design with 2x2 conditions combining 5 sessions of (A) tDCS on the dlPFC (anode on the right and cathode on the left, active 2mA vs sham 0mA) simultaneously to (B) an inhibition cognitive training (ICT) type Go/Nogo (specific vs non-specific). The specific ICT consisted to associate the Nogo with alcohol images and Go with sports images. There were also neutral images associated with 50% of Go. While non-specific training had only neutral images. Results showed a decrease in relapse's rate two weeks after treatment due to real tDCS combined with ICT. Moreover, we found out that real tDCS combined with specific ICT was more effective than real tDCS combined nonspecific ICT. Nevertheless, we did not find any significant effect on other clinical variables [craving (visual analog scale), symptoms of depression (BDI-II), anxiety (STAI-A), work memory (OSPA) and inhibition (Stop signal task)].

Following these results, one question still remains: Should tDCS be combined with ICT in order to be effective? To answer this question, we are conducting a new clinical trial with 5 sessions of tDCS on CPFDL (20minutes, anode on the right, left cathode) without an ICT. This study follows the same tDCS configuration as the previous one and takes place within the same multidisciplinary framework of treatment in order to compare our data.

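### The cross-study regression in section 3.5 cannot separate the effect of ICT from a change in relapse between the two studies, because ICT and study coincide for every patient.

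*Combined protocol and SAP*

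**What the plan says.** Section 1 (Background) describes the previous study: "We conducted a first clinical trial at Unit 72 Addictology of CHU Brugmann between 2017 and 2020". On its design: "The study had a design with 2x2 conditions combining 5 sessions of (A) tDCS on the dlPFC", active or sham, given simultaneously with "an inhibition cognitive training (ICT) type Go/Nogo (specific vs non-specific". All four cells therefore received a training. Non-specific training used neutral images only, but it was still a Go/Nogo training.

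The same section poses the open question, "Should tDCS be combined with ICT in order to be effective", and answers it with a new study: "we are conducting a new clinical trial with 5 sessions of tDCS on CPFDL (20minutes, anode on the right, left cathode) without an ICT". Recruitment is planned from about the end of March 2021 (section 3.2). Section 3.1 gives the allocation: "They will be randomly divided into two groups: the 'active' group (A) that will benefit from tDCS stimulation and the 'sham' group (S". During stimulation patients watch nature documentaries (section 3.3).

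Section 3.5, under the primary measurement, adds a final analysis: "in order to compare our two conditions to the four conditions of the previous study, we will perform a logistic regression with linear polynomial contrasts". The expected order is combined active tDCS with ICT, then tDCS only, then sham. No study, period or covariate term is named, and the text does not say how six cells become three levels. Section 4 (Benefits) promises of the study: "It will also compare whether tDCS is more effective alone or combined with cognitive training".

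**The concern.** Patients were randomised within each study and never between them. Knowing which study a patient was in tells you, without exception, whether that patient had ICT. Anything else that differs between a 2017-2020 cohort and a cohort starting in 2021 is then carried by the same comparison as ICT.

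At stake is the question that motivates the trial. If background relapse is higher now than it was then, tDCS with ICT will look better than tDCS alone even if ICT adds nothing. If it is lower, a real contribution of ICT could be hidden. Section 4 already announces the comparison without any caveat, and the cross-study regression is the only planned analysis that sets tDCS alone beside tDCS with ICT.

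**Working it through.** **Plan's own figures.** None is given for the cross-study analysis. The only sample-size figure, 60, matches the recruitment arithmetic of section 3.2 (12 months × 5 per month = 60).

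**Step 1: aliasing.** Code the six cells by study, tDCS and ICT.

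| Cell | Study | tDCS | ICT |
|---|---|---|---|
| Active, specific ICT | previous | 1 | 1 |
| Active, non-specific ICT | previous | 1 | 1 |
| Sham, specific ICT | previous | 0 | 1 |
| Sham, non-specific ICT | previous | 0 | 1 |
| Active | present | 1 | 0 |
| Sham | present | 0 | 0 |

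The correlation of ICT with the present-study indicator is -1. A model with intercept, tDCS, ICT and study has 4 columns but rank 3. With tDCS × ICT added it has 5 columns and rank 4. A study term therefore does not make the ICT main effect estimable.

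**Step 2: what the planned levels estimate.** With three equally spaced levels the linear weights are -1, 0, +1 (the plan gives none). The linear contrast is then combined minus sham, and tDCS only has zero weight. Whether it carries a between-study shift depends on who is in the sham level:

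- Present-study sham only: it carries the whole shift.
- Pooled sham: it carries part of it.
- Previous-study sham only: it carries none, but it then only repeats the previous study's active-versus-sham comparison.

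The step from combined to tDCS only always carries the whole shift.

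**Step 3: size of the distortion.** Assumptions, not in the documents: 20-30 patients per previous cell, so 40-60 per tDCS level; 30 per arm here; background relapse 40% previously. With no true effect of tDCS or ICT, the apparent odds ratio for combined versus tDCS only is (0.4/0.6) / (p/(1-p)), where p is relapse now:

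- p = 50%: 0.667/1.000 = 0.67
- p = 55%: 0.667/1.222 = 0.55
- p = 60%: 0.667/1.500 = 0.44

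With pooled sham the linear contrast is diluted. For 40 previous sham patients and p = 60%, pooled relapse is (16 + 18)/70 = 48.6%, and the apparent odds ratio is 0.667/0.944 = 0.71.

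**Step 4: false-positive rates.** Two-sided 5% Wald tests on the log odds ratio (0.5 added to each count), by exact enumeration of the binomial outcomes. Each entry is for 40 / 60 previous patients per level.

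| Relapse now | Linear, pooled sham | Linear, present sham only | Direct combined vs tDCS only, tDCS OR 0.4 in both studies |
|---|---|---|---|
| 40% | 4.7 / 4.7% | 4.4 / 4.2% | 4.0 / 3.9% |
| 50% | 6.6 / 6.4% | 12.5 / 13.6% | 11.3 / 13.1% |
| 55% | 9.2 / 8.7% | 22.6 / 25.4% | 20.0 / 23.6% |
| 60% | 12.9 / 12.0% | 36.5 / 41.5% | 32.8 / 38.6% |

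The two linear columns assume no true effects. With no true effects the direct test has the same rates as the present-sham column, so its full range over both settings is about 11-42%. With previous sham only, the linear contrast stays at 5.0-5.2%.

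**Step 5: the alternative.** Take (active - sham, previous) minus (active - sham, present) on the log-odds scale. A common shift cancels: by simulation (20,000 runs per setting) its false-positive rate is 4-5% throughout. That holds because the simulation lets only background relapse differ.

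Precision, with OR 0.4 with ICT, 1.0 without, and 40% background in both studies: relapse in the previous active group is (0.4 × 0.667)/(1 + 0.4 × 0.667) = 21.1%, and SE = √Σ 1/(n·p·(1-p)).

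- 40 per level: √(0.150 + 0.104 + 0.139 + 0.139) = 0.73
- 60 per level: √(0.100 + 0.069 + 0.139 + 0.139) = 0.67

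The log ratio of odds ratios is |ln 0.4| = 0.916, so approximate power is Φ(0.916/0.73 - 1.96) = 24% and Φ(0.916/0.67 - 1.96) = 28%. Simulation gives about 23-28%.

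**The case against.** The plan has a case. The new trial deliberately keeps the same unit, tDCS configuration and treatment framework so that the data can be compared. None of the hypotheses in section 2 concerns ICT, and the cross-study model comes last. A positive randomised active-versus-sham result here would by itself show that tDCS can work without ICT, with no cross-study model. All of this stands and limits the severity. But shared conditions are a design similarity and do not fix background relapse across non-overlapping recruitment periods. A null result here would leave the motivating question to the cross-study model.

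Some stronger readings are tempting and go beyond the documents:

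- *The 11-42% is the error rate of the planned analysis.* It belongs to a direct pairwise test that section 3.5 does not name. The named linear contrast gives about 6-13% or about 13-42%, depending on a sham mapping that the plan leaves open.
- *Every weighting of the levels carries the shift.* A linear contrast with previous-study sham only does not.
- *Adding a study term is enough.* Step 1 shows that the ICT effect stays inestimable.
- *The tDCS by study comparison is a clean test of ICT.* It remains aliased with any other between-study difference that modifies the tDCS effect.
- *Exclusions, ascertainment or case mix changed.* The documents do not describe these for the previous study. Apart from ICT itself, the documented differences are calendar period and what patients did during stimulation.

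**Conclusion.** The point holds as a should-fix. The aliasing of ICT with study follows from the documents and needs no assumption. The planned regression, with no study term and no stated sham mapping, cannot attribute a difference between tDCS with ICT and tDCS alone to ICT. The size of the error is illustrative. The 10 to 20 point change in background relapse and the previous arm sizes are assumptions, and with no change all the tests are close to 5%.

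A reader might infer that the trial's main relapse result is compromised. It is not: the randomised active-versus-sham regressions and the survival comparison use present-trial patients only. Nor does the alternative rescue a firm answer on ICT. With a standard error of about 0.67-0.73, its 95% interval extends by a factor of about 3.7 to 4.2 either way (exp(1.96 × 0.67) and exp(1.96 × 0.73)).

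**What to change.** In section 3.5, replace the pooled-level contrast with a logistic regression of relapse on tDCS, study and tDCS × study, with specific and non-specific ICT as separate strata of the previous study. Each study's sham arm serves as control for its own active arm only. Report the active-versus-sham odds ratio within each study, and their ratio with a confidence interval.

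In section 4, replace the sentence promising the comparison with a statement that it is an exploratory, non-randomised, indirect comparison. State its limits. It can be read as the contribution of ICT only if no other between-study difference modifies the tDCS odds ratio, and as combined versus alone only if ICT has no effect under sham. State its low precision as well.

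The cost is wording in two sections and no new data. The price is a wider interval, because both sham groups enter the comparison; low power even if ICT were fully necessary; and a more modest claim. The text should be settled before the cross-study data are analysed.
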